# **PROTOCOL**

Supplementation with a multi-strain probiotic formulation (Bio-Kult®) in the management of diarrhoea-predominant irritable bowel syndrome - a randomized, double-blind, placebo-controlled clinical trial

#### **ABSTRACT**

**Background:** Irritable Bowel Syndrome (IBS) is a common functional gastrointestinal disorder. Common clinical manifestation include abdominal pain, bloating, altered bowel habit which bears a great impact on the quality of life of an individual. Previously limited number of studies carried out in our country to assess the effect of probiotics on IBS patients which yielded mixed results. Further study preferably with larger sample and longer duration was recommended. Aims and objectives: This study aims to see the effect of probiotics on IBS.

Material and method: This is a controlled randomized clinical trial. The patient will be selected on the basis of Rome III criteria. IBS patients with a sample size of 400 will be taken. Purposive non probability method of sampling will be employed. In this method the patients who will be readily available and in close proximity will be selected according to the selection criteria. Patient will be collected from gastroenterology outpatient department. After full explanation of the study procedure, informed written consent will be taken. Participants will be randomized to receive either probiotics (Biocult®, Sandooz Bd. Ltd.) with standard treatment or only standard treatment for 8 weeks. All participants will be interviewed with baseline symptom score. Similar interview for symptom score will take place at 1 month interval for 3 times (including 1 month post treatment). All data will be processed by the SPSS program values will be expressed as frequencies or mean±SD unless otherwise mentioned. Between groups analysis will be done by Chi-square test, unpaired or paired students t-test as applicable; while predictive values will be seen by regression analysis. Only P values <0.05 will be considered as significant.

**Result:** This study will see the effect of two months use of probiotics on IBS and thereby highlight over the longer treatment of IBS.

## INTRODUCTION & BACKGROUND

Irritable Bowel Syndrome (IBS) is the most common functional disorder in clinical practice (Thompson WG et al.1992). IBS is characterized by abdominal pain, bloating and change in stool frequency and consistency in the absence of an organic cause. Although the prevalence has not been firmly established, it has been estimated that IBS affected 14-24% of women and 5-15% of men in western countries. The worldwide prevalence is approximately 10- 20% of the adult (Drossman et al.1993). IBS was shown to be more common in females in a rural community in Bangladesh. (Masud MA et al, 2001) Although the one year prevalence is about 19%, only a third present to their GPs (Jones R, Lydeard S, 1992). If the strict Rome III criteria for IBS are used, it affects around 5-11% of individuals, with similar prevalence in developed or developing countries (Guidelines--Rome III Diagnostic Criteria for Functional Gastrointestinal Disorders, 2006).

IBS may present at any age with peak prevalence in 30s and 40s - female predominance is most obvious in the 3rd decade and declines afterwards. (Spiller R et al, 2006). Symptoms may arise from the whole gut rather than just the colon. There is no structural lesion, but there appears to be a significant subgroup of patients in whom IBS is precipitated by an episode of bacterial gastroenteritis (Neal KR et al, 2002).

The pathogenesis of IBS is multi factorial, including roles for genetics, abnormal pain processing, behavioral pathways and the gastrointestinal microbiota (Chang JY et al. 2011). No specific diagnostic procedures identify IBS, because the underlying pathophysiology remains unknown. Thus, the diagnosis is dependent on symptoms and exclusion of major organic causes (Thompson WG et al.1989). A large case—

control study (Porter CK et al.2011) demonstrated that infectious gastroenteritis resulted in almost a fourfold increase in the odds of developing IBS within the subsequent 2 years. An imbalanced microbiota may contribute to GI symptoms through altered colonic fermentation resulting in increased formation of gas, an abnormal pattern of short chain fatty acid production and motility or sensitivity disturbances of the intestinal tract. The symptoms are not specific for IBS. The diagnosis of IBS rarely alters over time, but one always needs to be prepared to reconsider the diagnosis if the clinical picture changes. IBS has a significant negative impact on quality of life and social functioning in many patients, but it is not associated with the development of serious disease or with excess mortality. Although IBS is still considered as a functional disorder, there is increasing evidence that organic disease of the gastrointestinal tract (IBD), bacterial overgrowth, altered serotonin level and central dysregulation can be identified in subsets of patients.

Probiotics are supplements that are made up of live strains of beneficial bacteria. The Food and Agriculture Organization of the WHO provides the most widely accepted definition of probiotics as 'a live organism that, when ingested in adequate amounts, exerts a health benefit to the host' (FAO/WHO, 2001). There is growing body of opinion that the micro flora make up of the human body affects the overall health and risks for subsequent diseases. An imbalance of gut bacteria are thought to contribute to IBS symptoms. (Pimentel M et al. 2006).Restoration on the micro flora to normal conditions might reduce symptoms in those who suffer from IBS. Probiotics promote health by their ability to improve the micro flora in the gut, increasing numbers of beneficial species and reducing numbers of pathogenic bacteria.. Probiotics increase in trophic responses and regulate intestinal motility. Probiotics also modulate luminal

immunity by changing cytokine and cellular milieu from a pro inflammatory to anti inflammatory state. Probiotics regulate fermentation of non-degradable dietary fibre, intraluminal mucoproteins, favour lactose digestion and modulate intraluminal gas production (Douglas LC, Scanders ME, 2008). Evidence has accumulated to suggest the efficacy of certain probiotics which may be capable of bringing about a significant reduction in pain; abdominal distension and flatulence, while increasing health-related quality of life in IBS (M. Bixquet Jimenez, 2009). Several studies with L. acidophilus, S. thermophilus, L. plantarum have shown improvement of bowel symptoms in IBS patients (Sen S et al, 2002).

#### RATIONALE OF THE STUDY

Many drugs have been advocated in the treatment of IBS, for instance, spasmolytics, bulking agents, psychotropic agents, and 5-HT receptor antagonists. However, in many cases all these options remain disappointing for the relief of symptoms. The therapeutic efficacy in IBS is probably impacted by the heterogeneous pathogenesis of the disease which includes altered intestinal motility, visceral hypersensitivity, abnormal brain gut interaction, food intolerance, altered intestinal permeability and post infectious changes. Recently, the adverse role of alteration of gut micro flora at the onset of symptoms has been emphasized. Therefore, rationale exists for the therapeutic use of probiotics in IBS. In 2004-2005 a randomized, double blind placebo controlled trial (Kabir MA et al, 2011) on the effect of S. boulardii in diarrhea predominant IBS patients was conducted at BSMMU but the result was not satisfactory. Another study (Rahman MZ et al, 2013) at BSMMU during 2010-2011 with multistrain probiotics yielded a beneficial outcome which was significant both clinically and statistically. On both occasions, further study was suggested preferably with a larger sample size. These recommendations for further study prompted this study to be carried out in order to assess the effect of multistrain probiotics in relation to change of symptom scores in IBS patients and also to see changes of quality of life before and after the treatment. As per EMEA guideline, previous study (Spiegel B et al, 2009) revealed that abdominal pain is the most prevalent and distressing symptom in IBS patients and changes in the severity of pain were reflected as a more reliable outcome of successful treatment. IBS shouldn't be diagnosed in the absence of abdominal pain or discomfort. The pain or discomfort is typically relieved by

defecation or its onset is associated with an increased or decreased frequency of stool or looser or harder stool. The pain often is poorly localized, waxes and wanes, may be aggravated by eating & can occur in any part of abdomen; although it is more typically located in the lower abdomen. It can be referred to different areas in the abdomen or to the chest or back. Exacerbation of pain by stressful life events or difficult life situation is common. As abdominal pain is the hallmark feature of IBS and is recommended for the time being to assess the main symptomatology in at least partially validated scale. So, improvement of abdominal pain or discomfort along with abnormalities in defecation is considered as primary outcome. For other subtypes of IBS, and for "global" development programs intending to treat two or more subtypes, the use of the global assessment is, however, still recommended. Both endpoints should be evaluated as responder rates. The numerical evaluation of changes in scales is regarded to be a secondary endpoint. As per EMEA Guidance on The Evaluation of Medicinal Products for the Treatment of IBS, a responder has to demonstrate abdominal pain score which has improved at least 30% compared to baseline. Recent studies also show that there is high placebo response rate in functional bowel disorders which has a negative correlation with duration of study. So to overcome this confusion of high placebo response, this study is designed, unlike previous studies in our country, with a longer study period along with a larger sample size.

# RESEARCH QUESTION

Is multistrain probiotics with standard treatment more effective at reducing IBS symptoms than standard treatment of IBS?

# **OBJECTIVES OF THE STUDY**

# **Primary Objectives:**

- To assess the effect of multistrain probiotics on abdominal pain using a validated symptom severity score in IBS patients.
- 2. To assess the efficacy of a multi-strain probiotic supplement as a treatment option for IBS in a tertiary referral centre

# **Secondary Objectives:**

- To assess the effect of probiotics on global symptom severity scores which includes other symptoms of IBS (stool consistency, frequency, bloating) using a validated symptom severity score.
- 2. To assess changes in the use of rescue medication (i.e. laxatives or anti diarrhea medication such as Loperamide).
- 3. To assess any adverse events reported with probiotic use.

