#### **MATERIALS AND METHODS**

# a. Study Population:

Diagnosed cases of IBS using Rome III criteria.

Ethnicity - Bangladeshi

Age - 18-55 years

Sex - Male and female

b. Study design: Randomized controlled clinical trial.

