## Follow up schedule:

Participants will be followed up before intervention for baseline information and 1 month interval during treatment including 1 month post treatment.

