# k. Flow chart showing the sequence of tasks:

# 1. Procedures of preparing and organizing materials:

In people who meet the IBS diagnostic criteria, the following tests should be undertaken to exclude other diagnoses:

- Full blood count (FBC)
- Erythrocyte sedimentation rate (ESR) or C reactive protein (CRP)
- Antibody testing for coeliac disease
   (Endomysial antibodies [EMA] or tissue transglutaminase [TTG]).

Participants who fulfill the inclusion criteria in the absence of exclusion criteria will be included in the study. IBS patients will be diagnosed by translated and validated enhanced asian ROME III questionnaires in Bengali language for diagnosis of IBS. (Mohammed et al, 2014) Informed written consent will be obtained from participants. Data will be collected in questionnaire.

All the participants are advised to remain on their usual normal diet during the study period. Approximately total of 400 participants will be recruited in this study. They will be divided into two groups by randomization software, consisting of 200 in each group. One group will receive two capsules of probiotics (Bio-Cult, Sandors BD Ltd.) twice daily before or during a meal with standard treatment, while the other group will receive only standard treatment for 8 weeks.

Bio-Cult is a 14 strain probiotic formulation in a capsule form. Two capsules twice a day is equivalent to 8 billion CFUs (2 billion per capsule). The strains are-

[Bacillus subtilis PXN 21, Bifidobacterium spp. (B. bifidum PXN 23, B. breve PXN 25, B. infantis PXN 27,B. longum PXN 30), Lactobacillus spp. (L. acidophilus PXN 35, L. delbrueckii spp. Bulgaricus PXN39, L. casei PXN 37, L. plantarum PXN 47, L. rhamnosus PXN 54, L.helveticus PXN 45,L. salivarius PXN 57) Lactococcus Lactis PXN 63, Streptococcus thermophilus PXN 66].

Changes of symptoms will be assessed by using a previously used validated IBS instrument. (Richard Lea et al.2001). Symptom severity scoring system of IBS is shown in diagram-1 (C.Y. Francis et al. 1997). Symptom severity scores specially for abdominal pain, global symptom severity will be assessed as baseline and at 1 month

interval during treatment along with 1 month post treatment. This scoring will be done

on the basis of monthly interviews.

The collective scores to these individual domains give rise to the total score. The IBS-

SSS total score ranges from 0 to 500; a higher score indicating worse condition.

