## q. Intention to treat analysis:

After randomization, some patient may become non complaint to the allocated treatment and will be lost to follow-up. Randomization is a key process in a randomized controlled trial. So exclusion of this non complaint and drop out patients from the analysis of the result may create bias, reduce the sample size and thereby reduce the power of statistical tests and increase the probability of type II error.

Treatment group and control group will be analyzed with respect of their random allocation regardless of what will happen subsequently (whether they will actually receive the treatment or not).

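### Secondary objective 3 is worded for adverse events under probiotic only, and no section commits to asking about them in both arms or comparing the arms

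*Protocol*

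**What the plan says.** Item 3 of the Secondary Objectives reads "To assess any adverse events reported with probiotic use". No other sentence in the protocol text available mentions adverse events. There is no definition, no method of collection and no comparison between arms.

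The sections that bear on how item 3 would be carried out are these:

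- **Visits.** The follow-up schedule states: "Participants will be followed up before intervention for baseline information and 1 month interval during treatment including 1 month post treatment". It applies to participants generally, not to one arm.
- **What is done at visits.** Under Procedures of preparing and organizing materials, "Symptom severity scores specially for abdominal pain, global symptom severity will be assessed as baseline and at 1 month" intervals, with a further assessment one month after treatment. The same part of the protocol adds a concomitant-medication diary. Item o adds compliance checks by pack count and by questions on other medication and diet. No adverse-event question is listed for either arm.
- **Control.** The title describes "a randomized, double-blind, placebo-controlled clinical trial", and item b of Materials and Methods says "Randomized controlled clinical trial". The procedures allocate 1:1 ("They will be divided into two groups by randomization software, consisting of 200 in each group"), with one group on probiotic plus standard treatment, "while the other group will receive only standard treatment for 8 weeks".
- **Analysis.** The data-analysis section compares symptom scores. The intention-to-treat section says: "Treatment group and control group will be analyzed with respect of their random allocation regardless of what will happen subsequently".
- **Data sheet (Appendix I).** A group field is followed by items on pain, distension, stool form including watery, urgency, mucus, blood, and looser or more frequent stools with pain. Each is asked before treatment and at months 1, 2 and 3.

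**The concern.** A safety objective in a randomised trial is answered by the difference between the arms. Item 3 ties the events to exposure to the probiotic, and nothing else in the text turns it into a comparison. The control group is described as having standard treatment only, so staff could know who takes the probiotic. Recording events in that arm alone would then be feasible and consistent with the wording.

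A control rate matters here for two reasons found in the protocol itself. The Introduction characterises the disease by pain, bloating and changed bowel habit, so complaints will arise under either treatment. The section on confounding variables allows anxiolytics, antidepressants, spasmolytics, antidiarrhoeals and bulk-forming agents, which may produce events of their own. A count from the probiotic arm would mix these background events with any effect of the probiotic.

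What is asked at visits must be settled before data collection. A later analysis plan can choose how to tabulate events, but it cannot recover control-arm events that nobody asked about.

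**Working it through.** **Step 1: the plan's own figures.** The protocol gives no adverse-event rate and no safety calculation, so there is no safety figure to reproduce. The only figure needed is the arm size:

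- Per arm, with SD 87.77, difference 30, and z-values 0.84 and 1.96: 2 × 87.77² × (0.84 + 1.96)² / 30² = 134.2, rounded up to the stated 135.
- Adjusted total: 270 / (1 − 0.08 − 0.08)² = 382.7. The protocol gives 384 and takes 400, which is 200 per arm.

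The point does not depend on how 200 was reached.

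**Step 2: is the between-arm contrast supplied elsewhere?**

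- For symptoms, yes. The research question sets probiotic plus standard treatment against standard treatment, and the data-analysis section names a test for the symptom score.
- For rescue medication (secondary objective 2), the wording carries no restriction by arm.
- For adverse events, no section names a contrast, and the listed visit procedures contain no question on them.

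**Step 3: which events are affected?** Pain, distension and watery or loose stools are on the data sheet at baseline and at months 1, 2 and 3, without restriction by arm. These can be compared between arms from data already planned. What remains is any adverse event outside the symptom items.

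**Step 4: what is lost, and what two-arm recording would give.** Event rates are assumed, because the documents state none. With n = 200 per arm and the Wald method:

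- One arm alone: half-width = 1.96 × √(p(1 − p)/200).
- Difference with equal rates: half-width = 1.96 × √(2p(1 − p)/200).

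For example, at p = 0.10 the difference has half-width 1.96 × √(2 × 0.1 × 0.9/200) = 0.0588.

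| Assumed rate | One arm: half-width (points) | One arm: excess over control | Both arms: half-width of difference (points) |
|---|---|---|---|
| 5% | 3.0 | not estimable | 4.3 |
| 10% | 4.2 | not estimable | 5.9 |
| 20% | 5.5 | not estimable | 7.8 |
| 30% | 6.4 | not estimable | 9.0 |

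If 8% of each arm dropped out and contributed nothing, 200 × 0.92 = 184 would remain. The half-widths would then grow by a factor √(200/184) = 1.04, which leaves the picture unchanged.

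If the control rate were half the probiotic rate, the power to detect the difference at 200 per arm would be about 26%, 48%, 80% and 95% for probiotic rates of 5%, 10%, 20% and 30%. Two-arm recording therefore gives an estimate with a usable interval. It does not ensure that a modest excess among uncommon events is detected.

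**The case against.** The strongest reply is that item 3 is a statement of purpose, not a collection rule. The efficacy objectives are also phrased around the probiotic and are still compared between arms. Follow-up covers all participants, both groups are analysed as allocated, and under the double-blind placebo design in the title events could hardly be collected in one arm only. The bowel symptoms most in need of a control rate are already on the data sheet. How events are tabulated is ordinarily left to an analysis plan.

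Much of this stands:

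- No section says that control-arm events will not be collected. A reader might infer that the plan excludes them, but the text only leaves this open.
- A reader might also infer that events are noted only when patients volunteer them, or that the probiotic would look worse as a result. The documents state no mode of reporting and give no basis for a direction of bias.
- The protocol lists no expected adverse events of the probiotic, so no argument can rest on such a list.
- The data sheet cannot be said to lack an adverse-event field. Items 3 to 5 are not visible in the text available.

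Three parts do not stand. The efficacy objectives have their contrast made explicit elsewhere, and item 3 does not. The title does not secure two-arm collection, because the procedures describe a control group on standard treatment only; that contradiction needs reconciling in its own right. The intention-to-treat statement governs how data are analysed, not whether adverse events are asked about.

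**Conclusion.** The point holds as a defect of wording and of stated procedure. Item 3 is tied to probiotic use, and no section available commits to recording adverse events in both arms or to comparing them. One-sided recording is therefore possible under the text. If it happened, no excess over control could be estimated, at any event rate, for adverse events beyond the symptom items. With both arms of 200 recorded, the risk difference would have a 95% half-width of 4.3 to 9.0 points for assumed equal rates of 5% to 30%.

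It would go too far to say that the safety objective cannot be answered. The control group exists, it is seen on the same schedule, and its bowel symptoms are recorded monthly.

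The conclusion rests on the protocol text alone; the analysis plan was not available, and the appendix is incomplete in the text read. The event rates are assumptions. No efficacy figure or sample size is affected.

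**What to change.** - Reword secondary objective 3 as a comparison of adverse events between the randomised arms.
- Under Procedures of preparing and organizing materials, add one open adverse-event question, put in identical words to every participant in both arms at months 1, 2 and 3. Add a matching field to the data sheet if it has none.
- State that the number and percentage of patients with any adverse event will be reported by randomised arm, with the risk difference and its 95% confidence interval.

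The cost is one line in the objectives, one question per visit and a short reporting statement. No extra visit or participant is needed.

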#### **MATERIALS AND METHODS**

# a. Study Population:

Diagnosed cases of IBS using Rome III criteria.

Ethnicity - Bangladeshi

Age - 18-55 years

Sex - Male and female

b. Study design: Randomized controlled clinical trial.

### c. Main outcome variables to be studied:

Changes in abdominal pain for primary objective and overall symptom severity score as a secondary objective.

#### d. Checklist of Variables:

Height Weight

BMI DM

Psychological disorder(depression, anxiety)

